DESIGN: A nationwide stepped wedge cluster randomised trial in which primary care midwifery practices will be randomised.

PARTICIPANTS: 15,000 women who receive/continue care in the participating midwifery practice after the 20 week structural ultrasound and who have a singleton pregnancy.

INTERVENTION AND CONTROL STRATEGIES: In all midwifery practices, growth will be monitored using standardised symphysis fundal height (SFH) measurement. In the intervention strategy two routine US examinations will be performed (between 28-30 weeks and 34-36 weeks), while in the control strategy US examination will only be performed when clinically indicated. In both groups the IRIS consensus-based protocol will be followed if intrauterine growth retardation is suspected.

PRIMARY OUTCOMES: The clinical primary outcome is a dichotomous composite measure 'severe adverse perinatal outcome' up to 7 days after birth, including: perinatal death; Apgar score below 4 at 5 minutes after birth; impaired consciousness; need for assisted ventilation for more than 24 hours; asphyxia; septicaemia; meningitis; bronchopulmonary dysplasia; intraventricular haemorrhage; cystic periventricular leukomalacia; neonatal seizures or necrotizing enterocolitis. Also direct and indirect costs are primary outcomes.

SAMPLE SIZE: A total of 15,000 women in 60 midwifery practices; 7,500 women per strategy.

MAIN DATA ANALYSIS AND ECONOMIC EVALUATION: Multivariable logistic regression analyses, taking into account the clustered design. The economic evaluation will consist of a cost-effectiveness and a cost-utility analysis and will be performed from both a health care provider and societal perspective. We will base all primary analyses on intention to treat.

DURATION: 48 months.

Problem definition

DETECTION OF SMALL-FOR-GESTATIONAL-AGE

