The IRIS study is designed as a stepped wedge cluster randomised trial (c-RCT, Figure 1). A stepped wedge design is a type of crossover design in which different clusters cross over (switch treatments) at different time points. Clusters cross over in one direction only; typically from control to intervention. The time at which a cluster starts with the intervention is randomized; more than one cluster may start the intervention at a particular time point [Hussey 2007]. The advantages of a stepped wedge design are: a) all practices will offer the intervention for a shorter or longer period of time, which may encourage them to take part, b) practices will serve as their own control for a variable time period which will reduce the variation in characteristics and practice management between the intervention and control strategy group. Note: in contrast to many other stepped wedge c-RCTs the women participating in our study will receive the intervention strategy OR control strategy.

Midwifery practice will be the unit of randomisation. Randomisation per practice rather than per midwife or client has the advantage of minimising contamination and therefore maximising contrast between the intervention and control strategy group.

All midwifery practices (n=60) will start in the control strategy and provide obstetric care as usual. At intervals of 3 months, 33,3% of all practices (n=20) will change status from control to intervention group and will start offering the intervention, i.e. routine biometry ultrasound in the third trimester of pregnancy. To balance the number of women in the intervention and control group, practices will be stratified prior to randomisation in large and small practices, with the average practice size as the cut-

off point (i.e. 250 clients a year). Within these two strata, a computer-generated random sequence will determine the order in which practices move from control to intervention status. This randomisation will take place after practices have been recruited for participation in the study and before data collection begins.

Figure 1: The IRIS stepped wedge design | UC = control strategy; INT= intervention strategy; US= ultrasonography

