Clients will be recruited during months 1-12 (at 20-22 weeks gestation). During months 13-16 clients who are recruited last will receive their routine US (at 28-30 weeks and 34-36 weeks gestation). In month 17 the last IRIS study babies will be born. Follow-up measurement will take place in months 18-23.

SELECTION CRITERIA, RECRUITMENT, AND INFORMED CONSENT

Midwifery practices

Practices are eligible if they meet the IRIS study quality criteria of fetal ultrasonography. Furthermore, only practices where all midwives have received (or: agree to soon receive) the post registration training on the new KNOV guideline 'detection of IUGR' will be included in our trial.

Midwifery practices may show interest to participate in our RCT via a question in our nationwide survey on detection and management of suspected IUGR (sub-study A). Additionally, we will attend meetings of regional maternity care networks (the so-called VSVs) to inform and invite members to participate in our randomized trial. Other methods to inform midwifery practices about the IRIS study will be the post registration training sessions within the context of the new KNOV guideline; via the newly founded Midwifery Research Network Netherlands (MRNN) which is part of the midwifery consortium; articles in the journals of the national professional organisations; via social media.

All midwifery practices that show interest will be visited by a researcher who will inform them about the study's aims and procedures, will check if the practice fulfils the inclusion criteria, and if so, ask the midwives to sign a contract to show their commitment to the study protocol, in particular to the use of US according to randomisation status and use of the IRIS consensus-based protocol.

Pregnant women

In participating practices, pregnant women will be handed an information leaflet on the IRIS-study by their midwife during the first consultation after the 20 week screening test. Inclusion criteria: receiving/continuing care in the participating midwifery practice after the 20 week screening test and

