having a singleton pregnancy. The midwife will ask the woman if she is willing to participate in the IRIS study and if so, the midwife will ask her to sign the consent form. The form asks the woman's permission for using her personal data for merging data, for collecting detailed information from the woman's and her baby's client records, and for approaching her in the context of future sub-studies. An extra consent form will be added among the subsample of women who will fill in questionnaires. Consent forms will contain name, address, postal code, telephone number, and email and will be kept separate from other data files in a secure place.

Inclusion criteria: receiving

Women who do not have had a dating US will only be included if they have a reliable estimated data of delivery (EDD) based on the first day of their last menstrual period.

The NVOG guideline on US dating of pregnancy will be used for estimation of the EDD.

CONTROL AND INTERVENTION US STRATEGIES

Women in both US strategies will receive routine care as follows:

- Standardised SFH measurement
- Information about life style factors that may influence foetal growth, such as smoking, use of alcohol and drugs, and labour circumstances.
- Advise to report a reduction in fetal movements.
- US examinations on indication

Subsequent protocolised management will be according to the IRIS consensus-based protocol (to be developed in sub-study A).

Intervention US strategy

Additionally, two routine third trimester US examinations will be performed, one between 28 and 30 weeks and one 6 weeks after the first US. By performing two US examinations the growth pattern can be monitored. If a baby does not follow the expected curve, this may indicate a lack of growth even before the abdominal circumference or the estimated fetal weight is low. Subsequent protocolised management will be accomplished according to the IRIS consensus based guidelines.

PRIMARY OUTCOME - SEVERE ADVERSE PERINATAL OUTCOME

The primary clinical outcome is the occurrence of any severe adverse perinatal outcome up to 7 days after birth (yes/no). It concerns a dichotomous composite measure with 'yes' being defined as the presence of one or more of the following:

1. Antepartum, intrapartum or neonatal death occurring from 28 weeks gestation
2. Apgar score below 4 at 5 minutes after birth;
3. Coma, stupor or decreased response to pain;
4. Asphyxia, defined as cord blood arterial base excess of less than minus 12;

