Characteristics of midwifery practice, as presented in the latest LVR report

- number of midwives working in the practice
- number of clients per year
- proportion of nulliparous and multiparous women
- proportion of women per ethnic group
- proportion of home births
- rate of referral to secondary care

Characteristics of clients, collected by the midwife after the informed consent procedure:

- mother's date of birth, ethnic background, years of education, weight and height
- smoking (never, discontinued before current pregnancy, discontinued in first trimester, discontinued later in pregnancy; less than 10 cigarettes a day, 10-20, more than 20)
- alcohol use (no, discontinued before current pregnancy, discontinued in first trimester, discontinued later in pregnancy; sporadically, 0-2 units a day, more than 2)
- drug use (no, discontinued before current pregnancy, discontinued in first trimester, discontinued later in pregnancy; occasionally, daily, weekly, monthly)
- work status

Process measures

- % women declining participation
- % protocol violations
- % disagreements in primary outcome on verification by research assistant
- 3rd trimester US: intra-observer variability, inter-observer variability
- accuracy US: sensitivity, specificity of routine US to detect SGA
- Opinion of midwives towards effective and ineffective elements of intervention strategy

DATA COLLECTION

Existing databases

For all 15,000 women we will extract data from the following existing databases: 1) PRN database; 2) ultrasound centres' databases; 3) hospitals' patient records. These databases will be used to collect data on the primary clinical outcome 'severe adverse perinatal outcome' (e.g. Apgar score), obstetric variables, US scans (number, indication and findings, including biometry measures) and care processes (like number of days in hospital).

Forms and surveys

To collect data on variables that are not included in existing databases we will use the following forms and surveys.

Firstly, prior to onset of the study midwifery practices will fill in a short questionnaire on midwife practice characteristics as published in the practice's most recent LVR report.

Secondly, midwives will be asked to collect data on a small set of important prognostic variables for all women having signed the informed consent form (for example, on ethnicity, smoking, see p. 14).

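### On the protocol's own averages, the target of 15,000 women equals the practices' entire caseload, which leaves no margin for refusal or ineligibility before enrolment

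*Protocol*

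**What the plan says.** The synopsis (Sample size) states "A total of 15,000 women in 60 midwifery practices; 7,500 women per strategy". Four other places in the protocol bear on whether that number is available.

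- **Study design.** "All midwifery practices (n=60) will start in the control strategy", and "At intervals of 3 months, 33,3% of all practices (n=20) will change status from control to intervention group". Practices are stratified as large or small at the average practice size, given as "i.e. 250 clients a year".
- **Timeline under the design figure.** "Clients will be recruited during months 1-12", at 20 to 22 weeks of gestation.
- **Selection and consent of pregnant women.** A woman must be in the practice's care after the 20-week test and have a singleton pregnancy. If she has had no dating scan, she must have a reliable due date. Consent is individual and written: "The midwife will ask the woman if she is willing to participate in the IRIS study". The share of "women declining participation" is listed among the process measures.
- **Sample size of full trial.** The unadjusted requirement is 13,536. A design effect with an average cluster size of 250 and an ICC of 0.0003 raises it to 14,547. This is rounded up to 15,000 because some women who have signed consent may no longer be in the practice's care when the third trimester starts.

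**The concern.** The figure of 250 has two roles. In the design section it is a practice's yearly number of clients. In the sample-size section it is the number of trial women per practice. Over a 12-month recruitment period the two are equal only if every client is eligible and every eligible client signs.

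The protocol does not expect that. It has eligibility criteria, asks for individual consent and plans to count refusals, yet the calculation budgets nothing for any of these. The protocol criticises earlier trials as underpowered and presents its own size as a remedy. A foreseeable enrolment shortfall would bring part of that weakness back, and the document would still report 80% power.

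**Working it through.** **Inputs from the protocol.** Event rates 1.54% and 1.0%; significance level 0.05 (taken as two-sided); power 80%; 60 practices; 250 clients a year; 12 months of recruitment; ICC 0.0003; stated totals 13,536, 14,547 and 15,000.

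**Step 1: reproduce the plan's figures.**
- Two-proportion formula, pooled variance under the null, no continuity correction: 6,749 per arm, 13,498 in total. The stated 13,536 agrees to within 0.3%.
- Design effect: 1 + (250 − 1) × 0.0003 = 1.0747. Then 13,536 × 1.0747 = 14,547, as stated.
- Allowance: 15,000 − 14,547 = 453 women; 453 / 15,000 = 3.0%.
- Split: with 20 practices switching every 3 months, the control share is 60/60, 40/60, 20/60 and 0/60 over four quarters of 3,750 women. Control = 3,750 × 2 = 7,500, and intervention = 7,500, as stated.

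**Step 2: clients available.** 60 × 250 × 1 year = 15,000, the same as the number to be enrolled.

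**Step 3: share of clients that must be enrolled.**
- For the stated 15,000: 100%.
- For 14,547, with no loss after consent: 14,547 / 15,000 = 97.0%.
- For the unadjusted 13,536: 13,536 / 15,000 = 90.2%.

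**Step 4: what lower uptake gives.** The protocol states no uptake rate, so the range is assumed. With uptake u, N = 15,000 × u, cluster size m = N / 60, and effective N = N / [1 + (m − 1) × 0.0003]. Power comes from the formula of Step 1. The last column first removes the protocol's own 3% loss after consent.

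| Share of clients enrolled | N | Women per practice | Design effect | Effective N | Power | Power after 3% loss |
|---|---|---|---|---|---|---|
| 100% | 15,000 | 250 | 1.0747 | 13,957 | 81% | 80% |
| 95% | 14,250 | 237.5 | 1.0710 | 13,306 | 79% | 78% |
| 90% | 13,500 | 225 | 1.0672 | 12,650 | 77% | 76% |
| 80% | 12,000 | 200 | 1.0597 | 11,324 | 73% | 72% |
| 70% | 10,500 | 175 | 1.0522 | 9,979 | 67% | 66% |
| 60% | 9,000 | 150 | 1.0447 | 8,615 | 61% | 60% |

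The 100% row returns the stated 80% once the 3% loss is taken off, so the method matches the protocol's.

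**Step 5: what would close the gap.** Enrolling 15,000 at 90% uptake takes 15,000 / (250 × 0.9) = 67 practices, or 15,000 / (1,250 × 0.9) = 13.3 months. At 80% it takes 75 practices or 15.0 months. With 60 practices and 12 months kept, the mean caseload at 80% would have to be 250 / 0.8 = about 312 clients.

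**The case against.** The strongest reply is that the text does not define 250. It is called an average practice size and used as a stratification cut-off, without saying whether it counts all bookings or only women still in care after 20 weeks. On the second meaning, early losses and referrals already lie outside the 250. Nor does the protocol say that the recruited volunteer practices will average 250; larger practices could offset incomplete uptake. This stands. A reader might infer that 15,000 cannot be reached, but the document does not support that. It shows only that no margin is stated. Even on the narrower meaning, consent would still have to be complete.

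Two other stronger readings also fail. A reader might infer a calculation error, but every step of the sample-size chain and the 7,500/7,500 split reproduce. A reader might also say that loss is ignored altogether, but 3% is allowed for women who leave after consent. That allowance does not help here, because all 15,000 must first sign.

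It is also fair to say that the uptake range is assumed and that the effect is small at its upper end: about 79% power at 95% uptake. The large losses belong to the lower end. Finally, the effect of the stepped-wedge design and its time periods on power is a separate question. It should not be added to this point, and none of the figures above includes it.

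**Conclusion.** The point holds as a fault in recruitment planning. The stated number of practices, practice size and recruitment period yield exactly 15,000 clients, so the enrolment target, the cluster size of 250 and the 80% power all rest on complete eligibility and consent. The protocol's own consent procedure and process measures do not assume this.

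If 60% to 90% of clients are enrolled, power by the protocol's method falls to between about 61% and 77%, or between 60% and 76% after the 3% loss. The conclusion assumes that 250 is the mean yearly caseload of the participating practices. The size of the effect also rests on the assumed uptake range, the protocol's event rates, an ICC of 0.0003 and the simple design effect.

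**What to change.** In the synopsis and the sample-size section:

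1. State whether 250 counts all bookings or only eligible women in care after 20 weeks.
2. Replace it, as cluster size, with the expected number enrolled per practice: clients × share in care and eligible after 20 weeks × share consenting. Give the assumed rates and their basis.
3. Restate expected N, women per strategy and power over a participation range such as 60% to 90%, keeping the 3% loss after consent as a separate step.
4. Reconcile the result with 60 practices and 12 months. Either accept the lower N and power, or change the number of practices, the mean practice size or the recruitment period.

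If recruitment is lengthened, the switching schedule needs review too. At 80% uptake each quarter brings 12,000 / 4 = 3,000 women. A fifth quarter with all practices already switched would give 3,000 × 2 = 6,000 control and 9,000 intervention women, not 7,500 each.

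Restating the figures costs a few lines of text and a less favourable stated power, and needs no extra women. Restoring 15,000 would cost more practices or more time, as in Step 5 of the working.

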5. Neonatal seizures defined as clonic movements which cannot be stopped by holding the limb, occurring on two or more occasions before 72 hours of age;
6. Assisted ventilation for more than 24 hours via endotracheal tube initiated within 72 hours after birth;
7. Septicaemia, ascertained by a positive blood culture;
8. Meningitis, ascertained by positive cerebrospinal fluid culture;

9. Bronchopulmonary dysplasia (BPD), defined as need for oxygen at a postnatal gestational age from 36 completed weeks as well as an X-ray compatible with BPD;
10. Intraventricular hemorrhage, defined as grade 3 or 4 and diagnosed by cranial US or at autopsy;
11. Cystic periventricular leukomalacia (PVL), diagnosed by cranial US or at autopsy showing periventricular cystic changes in the white matter excluding subependymal and choroid plexus cysts;
12. Necrotizing enterocolitis, defined as either perforation of intestine, pneumatosis intestinalis or air in the portal vein, diagnosed by X-ray, surgery, or at autopsy;

Cord blood arterial base excess was chosen as an indicator of asphyxia because, unlike pH, it is linearly related to the degree of metabolic acidosis which is a better indicator of asphyxia than measures of respiratory acidosis [Ross & Gala, 2002]. There was some discussion in the expert and project group on the use of Apgar scores in the composite outcome. Apgar score in itself is not comparable to the other outcomes, which are more predictive of long term severe adverse outcomes. However, in the Netherlands, a quarter of all women still give birth at home. Suspected SGA is a reason for referral to specialist care and routine US may lead to more SGA babies being born in hospital. Nevertheless, unexpected poor outcomes may occur at home and blood gases immediately after birth will then not be available. In hospital too, cord blood samples may be forgotten or go missing. We have chosen a low cutoff point for Apgar score at five minutes (below 4) in which case most babies will have other adverse outcomes as well. In a recent Dutch RCT on the management of pregnancies complicated by SGA, Apgar scores were also part of the composite outcome [Boers et al., 2010]. Low birth weight is not part of the primary outcome because this is not a measure of morbidity but rather a factor that is associated with morbidity such as respiratory problems. Also, premature labour may sometimes be induced to prevent stillbirth even though prematurity is associated with low birth weight.

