Given the above mentioned ICCs for neonatal mortality, the formula to correct for clustering $[1 + (n-1) * ICC]$ with $n = 250$ (i.e. average cluster size) gives a required sample size for the IRIS study of 14,547 (ICC 0.0003) to 20,304 (ICC 0.002). For two reasons we expect the ICC in the IRIS study to be much more similar to 0.0003 than to 0.002. Our first argument is that the ICCs reported in the paper of Pagel et al. (2011) are based on prevalence rates ranging from 1.5% to 5.9% which is higher than the expected severe perinatal outcome in the IRIS study. As ICCs are associated with the prevalence of the outcome of interest [Pagel et al., 2011] we may expect the ICC in the IRIS study to be even lower than 0.0003. Our second argument is that midwife practices will offer both the control strategy (i.e. US on indication) and, later on, the intervention strategy (i.e. routine US). This will reduce the variation in characteristics and practice management between the intervention and control strategy group and thereby lower the size of the ICC .

Taking into account an ICC of 0.0003, the required sample size is 14,547 women. As not all women who will sign the informed consent form may receive care in the participating midwifery practice at the start of the third trimester, we adjusted this figure to a total of 15,000.

Effectiveness analyses

Firstly, we will assess the similarity between baseline characteristics of women having had the intervention strategy and women having had the control strategy. Secondly, we will compare baseline characteristics of drop-outs and completers by using logistic regression analysis. Thirdly, we will use multivariable logistic multilevel analyses to investigate the effect of routine US screening on perinatal outcome, adjusting for possible clustering of observations and confounders (e.g. ethnicity, maternal age, weight and height, smoking, alcohol use, drug use, blood pressure). We will base our analyses on intention to treat and set the level of significance at $p < 0.05$.

We will perform a subgroup analysis for women without US indication and for nulliparous women.

In addition to the intention to treat analysis we will also perform a per-protocol analysis, restricted to the women in the intervention group who received the two US examinations and to the women in the control group who did not receive any screening US.

Cost-effectiveness and cost-utility analyses

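### The primary composite sets a 28-week floor for deaths but none for its other eleven components, so births before 28 weeks are scored inconsistently and with events that precede the intervention

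*Protocol*

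**What the plan says.** The Protocol section on the primary clinical outcome makes the composite positive if any one of 12 components is present up to 7 days after birth. Component 1 is "Antepartum, intrapartum or neonatal death occurring from 28 weeks gestation". The others have no gestational floor. Examples are "Apgar score below 4 at 5 minutes after birth", "Assisted ventilation for more than 24 hours via endotracheal tube initiated within 72 hours after birth" and "Intraventricular hemorrhage, defined as grade 3 or 4 and diagnosed by cranial US or at autopsy". The bronchopulmonary dysplasia item mentions 36 weeks ("defined as need for oxygen at a postnatal gestational age from 36 completed weeks"), but that is the age at which the diagnosis is made, not a limit on gestation at birth.

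The synopsis describes the same composite and lists perinatal death with no 28-week limit.

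Three other places matter:

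- Study design: women are recruited at 20-22 weeks.
- Intervention US strategy: the only added element is two routine scans, the first between 28 and 30 weeks.
- Effectiveness analyses: analysis is by intention to treat, with no stated exclusion of pregnancies that end before 28 weeks.

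The sample size section raises 14,547 to 15,000 because not every consenting woman "may receive care in the participating midwifery practice at the start of the third trimester".

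**The concern.** Between recruitment and 28 weeks the components follow different rules. A fetal death in that interval is scored as no event; a live birth in the same interval with a counted complication is scored as an event. The worse result gets the better score, and the composite does not mean the same thing across the gestations it covers.

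The 28-week floor on deaths suits the design, because care under the two strategies is the same until the first routine scan. The same reasoning applies to morbidity from births before 28 weeks, yet that morbidity is counted. These events cannot respond to the intervention, so they add noise and pull the relative effect towards no difference. The composite is also the effect measure in both cost-effectiveness analyses, so the inconsistency carries into those ratios.

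This concerns the definition of the primary outcome, which the Protocol itself fixes and, between synopsis and main text, fixes in two ways.

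**Working it through.** **Scoring a pregnancy that ends at 26 weeks, as written**

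| Outcome at 26 weeks | Main text | Synopsis |
|---|---|---|
| Stillbirth | No event | Event if it is taken as a perinatal death; no limit given |
| Live birth, ventilated more than 24 hours | Event | Event |
| Live birth, grade 3 or 4 haemorrhage | Event | Not graded in the synopsis; haemorrhage listed |
| Live birth, death within 7 days | Not component 1; may count through another component | Event if it is taken as a perinatal death |

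Three qualifications:

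- Bronchopulmonary dysplasia cannot be met within 7 days by an infant born at 26 weeks. Apgar score, ventilation, sepsis and haemorrhage can.
- Some components may be diagnosed at autopsy. Unless such a finding were counted for a stillbirth, a stillbirth before 28 weeks meets no component.
- The text does not say whether the 28 weeks refers to gestation at birth or at death. Within the 7-day window this matters only for births from 27+0 to 27+6. For example, an infant born at 27+3 who dies on day 5 (28+1) counts on one reading and not on the other.

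**Reproducing the Protocol's sample size**

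Inputs from the sample size section: 1.54% versus 1.0%, 80% power, significance level 0.05 (taken as two-sided), ICC 0.0003, cluster size 250.

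- Pooled two-proportion formula without continuity correction, with p̄ = 0.0127 and difference 0.0054: n = [1.96·√(2p̄(1−p̄)) + 0.8416·√(p1(1−p1)+p2(1−p2))]² / 0.0054² = 6,749 per group, 13,498 in total. The stated 13,536 is within 0.3%.
- Design effect: 1 + 249 × 0.0003 = 1.0747. Then 13,536 × 1.0747 = 14,547, as stated.

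**Baseline power at 15,000 women**

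- Effective n per group: 7,500 / 1.0747 = 6,979.
- Power = Φ{[d − 1.96·√(2p̄(1−p̄)/n)] / √[(p1(1−p1)+p2(1−p2))/n]} = 81.3%.
- Expected events: 7,500 × 0.0154 + 7,500 × 0.010 = 115.5 + 75 = 190.5.

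**Effect of unmodifiable events before 28 weeks (assumed range)**

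The documents give no rate, so let x be the share of all women with such an event.

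- Case A: x is added to both rates, giving 1.54% + x versus 1.0% + x.
- Case B: x already lies inside the 1.54%, and only the rest falls by the planned ratio. The intervention rate is x + (1.54% − x) × 1.0/1.54.

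| x | Events per 15,000 | Power, case A | Power, case B |
|---|---|---|---|
| 0.02% | 3 | 80.7% | 80.2% |
| 0.05% | 7.5 | 79.8% | 78.4% |
| 0.10% | 15 | 78.4% | 75.4% |
| 0.20% | 30 | 75.5% | 68.6% |

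At x = 0.20% the risk ratio moves from 1.00/1.54 = 0.65 to 1.20/1.74 = 0.69 in case A, and to 1.07/1.54 = 0.69 in case B.

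**What a common floor recovers**

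In case A the floor restores 81.3%. In case B it restores only part, because the modifiable rate was lower than planned from the start. At x = 0.20% the comparison becomes 1.34% versus 1.34% × 1.0/1.54 = 0.87%, and power is 75.7% rather than 68.6%.

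**The case against.** **Size.** The number of affected births rests on rates that the Protocol does not give. At the low end of the range the loss is under one or about one percentage point of power, and even at 30 events the risk ratio moves only from 0.65 to about 0.69. This stands: the table is conditional, and no single share of primary events can be put forward as the estimate.

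**Already covered.** The increase from 14,547 to 15,000 adds 453 women to allow for those not in practice care at the start of the third trimester. This suggests that a third-trimester population was in mind, and an analysis set defined that way would remove most of the mismatch. It is, however, an allowance for loss and not an exclusion rule. The analysis set may properly be left to the SAP, which is not at hand. The wording of the components, and its disagreement with the synopsis, belongs to the Protocol.

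**Bias.** A reader might infer that the uneven floor favours one strategy. The documents do not support that. The events in question precede the first routine scan, and nothing stated would make them more frequent under either strategy.

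**Remedy.** It is tempting to restrict the primary analysis to women still in the practice's care at 28 weeks. That would bring in a new problem. Allocation is by practice, no concealment of a practice's status is described, and leaving or being referred before 28 weeks could depend on whether routine scans are coming. Such a restriction also fits poorly with intention to treat.

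**Conclusion.** The inconsistency is plain on the text: one of 12 components has a gestational floor, the other eleven have none, and the synopsis omits it. The consequence is dilution and an unclear composite, not demonstrated bias.

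The size is uncertain. Over an assumed range of 3 to 30 unmodifiable events per 15,000 women, power falls from 81.3% to between 80.2% and 80.7% at the low end, and to between 68.6% and 75.5% at the high end. Planned power has little margin, so about 7.5 such events bring it below 80% in either case. These figures use the Protocol's own simple comparison with a design effect of 1.0747 and two-sided 0.05. The number of events is an assumption throughout.

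This should be corrected. It does not by itself threaten the trial.

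**What to change.** 1. Apply one gestational floor to all 12 components: 28+0 weeks, which component 1 already uses, based on gestation at birth or at fetal death. Pregnancies that end earlier contribute no primary events and are reported descriptively.
2. Do not make remaining in the practice's care a condition.
3. State whether the floor in component 1 means gestation at birth or at death. Gestation at birth or fetal death gives one rule that serves every component.
4. Align the synopsis with the main text.
5. Confirm that the 1.54% taken from the national perinatal registry (PRN) uses the same definition and the same floor. If not, re-derive it and repeat the sample size calculation.

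The first four items change wording only and need no new data. A few early events leave the primary outcome. The fifth item may require a new registry extraction. If early births were included in the 1.54%, the corrected rate will be lower, and the floor will recover only part of the lost power.
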